Sample Size Calculation: The sample size is determined empirically. Xiidra achieved a 0.25 unit difference between lifitegrast ophthalmic solution and vehicle in mean change from baseline to day 84 in inferior cornel staining and a standard deviation of approximately 0.75 in Phase 2. Sample sizes for this study are based on detecting a 0.35 unit difference between the active and vehicle groups, assuming a standard deviation of 0.75. In Stage 1 the number of expected enrolled subjects varies between 43 and 53 subjects in the active group and between 37 and 47 subjects in the vehicle group. In Stage 2 the number of expected enrolled subjects is 60 in the active group and 30 to 60 subjects in the vehicle group. Thus, the combined sample provides between 103 and 113 subjects in the active group and between 67 and 77 subjects in the matching vehicle group or between 97 and 107 subjects in the combined vehicle group. Under these assumptions and allowing a dropout rate of 10%, sample sizes of 93 in the active treatment group and 60 in the vehicle group will yield 80% power to show a significant difference at the $\alpha = 0.05$ level using a two-sample t-test.

Summary of Known and Potential Risks and Benefits to Human Subjects

AXR-159X has previously been well tolerated clinically when administered via oral inhalation or intranasal routes to healthy volunteers, asthma and allergic rhinitis patients. This is the first time that a competitive antagonist of the $\alpha 4$ subunit, $\alpha 4\beta 1$ and $\alpha 4\beta 7$ integrins, (AXR-159 Ophthalmic Solution) is being administered as an eye drop in humans. The eye drop formulation was very well tolerated in preclinical species (i.e., rabbits, dogs) when administered at 50 mg/mL up to 12 times per day for up to 3 months. Eye drop administration can be expected to produce negligible systemic levels of drug.

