6 OVERALL STUDY DESIGN

6.1 Overall Design

This is a multicenter, double-masked, vehicle-controlled, randomized, parallel group study carried out in 2 stages (Stage 1: AXR-159 Ophthalmic Solution (30 mg/mL or 50 mg/mL) dosed three-times daily (TID) or twice-daily (BID); Stage 2: AXR-159 Ophthalmic Solution (3 mg/mL, 30 mg/mL or 50 mg/mL) dosed three-times daily (TID) or twice-daily (BID)).

For both Stages 1 and 2, patients with signs and symptoms of DED will be randomly assigned in a 1:1 (Stage 1) or up to a 2:2:2:2:1:1:1 (Stage 2) ratio to receive either a single concentration of AXR-159 Ophthalmic Solution or AXR-159 Ophthalmic Solution Vehicle. A screening visit will be followed by a baseline period where subjects will dose with AXR-159 Ophthalmic Solution Vehicle for 14 days. At the end of the baseline period patients who still exhibit signs and symptoms of DED will be enrolled into a 3-month treatment period (See [Appendix 1](#) for study visit structure across Stages 1 and 2 and [Figure 6.1-1](#) for the study flow diagram). If only a single dosing regimen is selected for Stage 2 a 1:1:1:1 regime may be selected: AXR-159 Ophthalmic Solutions and AXR-159 Ophthalmic Solution Vehicle.

[figure not shown]
When the 10th patient enrolled in Stage 1, Cohort 1 (8 patients on AXR-159 Ophthalmic Solution 50 mg/mL TID and 2 patients on vehicle TID) completes the Week 2 visit, a Data Review Committee (DRC) will evaluate all available safety data. If AXR-159 Ophthalmic Solution 50 mg/mL TID is safe and well tolerated the DRC will recommend

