expansion of the AXR-159 Ophthalmic Solution 50 mg/mL and vehicle TID groups (N = 45 per group) and to halt the initiation of Stage 1, Cohorts 2 and 3. If AXR-159 Ophthalmic Solution 50 mg/mL TID is NOT safe and well tolerated the DRC will recommend Stage 1, Cohort 2 (8 patients on AXR-159 Ophthalmic Solution 30 mg/mL TID and 2 patients on vehicle TID) and to halt the Cohort 1 Expansion Cohort. Patients already enrolled in Stage 1, Cohort 1 will continue at the investigator's discretion. Any patients that discontinue during the study will be followed through the resolution of their adverse event(s) or end of study. When the 10th patient enrolled in Stage 1, Cohort 2 completes the Week 2 visit, a DRC will evaluate all available safety data. If AXR-159 Ophthalmic Solution 30 mg/mL TID is safe and well tolerated the DRC will recommend expansion of the AXR-159 Ophthalmic Solution 30 mg/mL and vehicle TID Expansion Cohort (N = 40 per group) and to halt Cohort 3. If AXR-159 Ophthalmic Solution 30 mg/mL TID is NOT safe and well tolerated the DRC will recommend Stage 1, Cohort 3 (8 patients on AXR-159 Ophthalmic Solution 30 mg/mL BID and 2 patients on vehicle BID) and to halt the Cohort 2 Expansion Cohort. Patients already enrolled in Stage 1, Cohort 2 will continue at the investigator's discretion. When the 10th patient enrolled in Stage 1, Cohort 3 completes the Week 2 visit, a DRC will evaluate all available safety data. If AXR-159 Ophthalmic Solution 30 mg/mL BID is safe and well tolerated the DRC will recommend expansion of the AXR-159 Ophthalmic Solution 30 mg/mL and vehicle BID Expansion Cohort (N = 35 per group). If AXR-159 Ophthalmic Solution 30 mg/mL BID is NOT safe and well tolerated the DRC will recommend stopping the study. Thus, in stage 1 a successive cohort will only be started if the previous cohort is felt to be either unsafe or poorly tolerated by the DRC.

When the last patient enrolled in Stage 1 completes the Month 3 visit in the Expansion Cohort, a formal Interim Analysis will be completed and the DRC will evaluate all available safety and efficacy data from Stage 1 before recommending initiation of Stage 2. Stage 2 is a parallel group design and the DRC may recommend up to a maximum of 7 groups as depicted in [Figure 6.1-1](#). Groups that are either unsafe, poorly tolerated, or likely futile may be discontinued by the DRC. The DRC may reallocate patients to the surviving AXR-159 Ophthalmic Solution dose groups.

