10.1.4 Procedures for Final Study Entry

Subjects must meet all inclusion and none of the exclusion criteria.

10.1.5 Methods for Assignment to Treatment Groups:

Prior to initiation of study run-in (at Visit 1), each subject who qualifies for entry will be assigned a screening number. All screening numbers will be assigned in strict numerical sequence at a site and no numbers will be skipped or omitted. If all inclusion and exclusion criteria are met at Visits 1 and 2, each qualifying subject will then be assigned a randomization number at the end of Visit 2.

A randomization schedule will be provided to each investigational site. The randomization schedule will use block randomization stratified by site, such that there will be an approximate equal number of subjects assigned to each of the two treatment arms at each site for the Stage 1, Expansion Cohort. For Stage 1, Cohorts 1-3 patients with signs and symptoms of DED will be randomly assigned in a 4:1 ratio to receive either a single concentration of AXR-159 Ophthalmic Solution or AXR-159 Ophthalmic Solution Vehicle. The site staff will dispense to the patient the study kit labelled with the corresponding randomization number. The randomization number will be recorded on the patient's source document and eCRF. New kits will be dispensed at Visits 2, 3, and 4 based on the subject's randomization. The Sponsor, Investigators, and study staff will be masked during the randomization process and throughout the study.

During the run-in period, the patients will all be supplied with AXR-159 Ophthalmic Solution Vehicle. Patients will be informed that they will receive only vehicle during the 2-week run-in period. Following the run-in period the patient, site personnel, the sponsor and patients will be masked to the treatment assignment for the 3 month treatment period. All study medication will be provided in identical unit of dose vials and cartons to maintain masking of the study.

For both Stages 1 and 2, patients with signs and symptoms of DED will be randomly assigned in a 4:1 (Stage 1, Cohorts 1-3) ratio, a 1:1 (Stage 1, Expansion Cohort) ratio, or to a 2:2:2:2:1:1:1 (Stage 2) ratio to receive either a single concentration of AXR-159 Ophthalmic Solution or AXR-159 Ophthalmic Solution Vehicle.

For the expansion cohort in Stage 1 and Stage 2, subjects will be randomized by strata as follows:

- Site
- Baseline eye dryness score ≥ 60 , < 60
- Baseline inferior corneal staining > 1.5 , ≤ 1.5

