12.4 Statistical Analyses

12.4.1 General Approach

In general, continuous data will be summarized with descriptive statistics (number of subjects, mean, standard deviation, median, minimum, and maximum) and will be analyzed using analysis of variance (ANOVA), analysis of covariance (ANCOVA) techniques, two-sample t-tests or Wilcoxon rank sum tests for between-group comparisons, and paired t-tests or sign-rank tests for within-group analyses. Categorical variables will be summarized by number of subjects (n), frequency counts, and percentages, and they will be analyzed using Pearson's chi-square test or Fisher's exact test (if the expected cell count is less than 5 in 25% or more of the cells). Ordinal variables will be analyzed using the Cochran-Mantel-Haenszel (CMH) or the Wilcoxon rank-sum test for between-treatment comparisons and the sign-rank test for within-treatment comparisons.

All summaries will be presented by treatment group and visit. Summaries will be provided for demographics, baseline medical history, concurrent therapies, and subject disposition.

For the purpose of summarization, medical history, concurrent therapies, and adverse events will be coded to MedDRA and WHO Drug dictionaries, as appropriate.

Baseline measures are defined as the last measure prior to the initiation of study treatment, usually at Day 1. If a measure is taken both pre-CAE® and post-CAE®, the baseline will be the last time point matched value prior to the initiation of study treatment. For post-CAE® measures, this will be at Day -14. For changes from pre-CAE® to post-CAE® post first treatment, the change from pre-CAE® to post-CAE® at Day -14 will be considered the baseline value.

Changes from baseline will be calculated as visit – baseline and summarized by treatment and visit as described above. Treatment comparisons between an active treatment and vehicle will be calculated as active – vehicle.

All primary and secondary analyses will be two-sided at a significance level of 0.05. 95% confidence intervals will be provided where appropriate.

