13.1.1 PRE-CAE[®] INFERIOR FLUORESCEIN STAINING (ORA CALIBRA[®] SCALE)

Pre-CAE[®] fluorescein staining in the inferior region of the cornea will be graded using the Ora Calibra[®] Corneal and Conjunctival Staining Scale. The Ora Calibra[®] Corneal and Conjunctival Staining Scale ranges from 0 to 4 (half grade increments may be used), where grade 0 = none, 1 = trace, 2 = mild, 3 = moderate, and 4 = severe.

Changes from baseline in the pre-CAE[®] inferior fluorescein staining scores will be summarized at Visit 5 (Day 85 ± 2) by treatment group for the study eye using quantitative summary statistics. Changes from baseline will be compared between each AXR-159 Ophthalmic Solution group versus vehicle group at matched dosing frequency (TID or BID) using an ANCOVA model that adjusts for baseline. Specifically, the ANCOVA model will include terms for baseline inferior corneal staining score (ICCS) and baseline eye dryness score as covariates and treatment group as a factor in the model. The differences in means, two-sided 95% CIs for the difference in means and p-values will be reported. Pairwise t-tests from the ANCOVA model will be used to compare treatment and vehicle groups.

The following SAS code will be used to run the ANCOVA analysis for each of Stage 1 and Stage 2:

```
PROC MIXED DATA = INDATA;
```

```

CLASS TREATMENT;
MODEL CHANGE_ICSS = BASELINE_ICSS BASELINE_EDS TREATMENT
   / SOLUTION COVB;
LSMEANS TREATMENT / CL PDIFF;
ODS OUTPUT LSMEANS = OUTLS DIFFS = OUTDIFFS;
RUN;

```

where

- *TREATMENT* is the name of the treatment group variable
- *BASELINE_ICSS* is the baseline pre-CAE® inferior fluorescein staining score in the study eye
- *BASELINE_EDS* is the baseline pre-CAE® eye dryness score
- *CHANGE_ICSS* is the pre-CAE® inferior fluorescein staining in the study eye at Visit 5 (Day 85 ± 2) – *BASELINE_ICSS*
- *OUTLS* is the name of the output dataset that contains the statistical results for the treatment means from the ANCOVA model
- *OUTDIFFS* is the name of the output dataset that contains the statistical results for the differences in treatment means from the ANCOVA model

T-tests and Wilcoxon rank sum tests will also be conducted as sensitivity analyses to assess robustness of the results.

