13.2.1 UNANESTHETIZED SCHIRMER'S TEST

Unanesthetized Schirmer's Test will be assessed on both eyes at all visits. Visit 1 and 5 assessments will be pre-CAE®. The Schirmer's test strip will be placed in the lower temporal lid margin of each eye. After 5 minutes, the test strip will be removed and the length of the moistened area will be recorded in millimeters (mm) for each eye. Lower values indicate less tears produced in the eye.

Unanesthetized Schirmer's Test will be summarized by treatment group and visit using quantitative summary statistics. Change from baseline will be also summarized.

Pairwise two-sample t-tests will be employed to compare treatment and vehicle means at each visit and time point. The differences in means, two-sided 95% CIs for the difference in means and p-values will be reported. Wilcoxon rank sum tests will also be conducted. Analyses will be performed on the mITT population with observed data only.

Changes from baseline will be compared between treatment groups using ANCOVA models that adjust for baseline value, baseline inferior corneal staining (Ora Calibra® scale) and baseline eye dryness (VAS). The differences in means, two-sided 95% CIs for the difference in means and p-values will be reported. T-tests and Wilcoxon rank sum tests will also be conducted. Analyses will be performed on the mITT population with observed data only.

Binary clinical cure variables will be defined by visit for Schirmer's test ≥ 5 mm, Schirmer's test ≥ 10 mm and Schirmer's change from baseline ≥ 5 mm, and will summarized by visit using number of subjects, frequency counts and percentages. Treatment groups will be compared pairwise with vehicle using Pearson's chi-square test or Fisher's exact test if the expected cell count is less than 5 in 25% or more of the cells. In addition, the proportion of responders will be compared between treatment groups using the Cochran-Mantel-Haenszel method stratifying by baseline ICSS (≤ 1.5 , > 1.5) and baseline eye dryness (< 60 , ≥ 60). For the Cochran-Mantel-Haenszel analysis of the combined Stage 1 and Stage 2 data, the study Stage will also be included as a stratification factor.

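### Stage 1 efficacy pools a 4:1 lead-in cohort with a 1:1 expansion cohort and has no term for randomisation phase: a small, avoidable bias of unknown direction

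*Protocol*

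**What the plan says.** **Design.** Protocol 6.1 opens Stage 1 with a lead-in cohort of "8 patients on AXR-159 Ophthalmic Solution 50 mg/mL TID and 2 patients on vehicle TID". Once the tenth lead-in patient has completed Week 2 and the DRC has reviewed safety, the same regimen expands by 45 per group. If a later cohort is needed, the expansion is 40 per group (after Cohort 2) or 35 per group (after Cohort 3). Protocol 10.1.5 states: "For Stage 1, Cohorts 1-3 patients with signs and symptoms of DED will be randomly assigned in a 4:1 ratio". It makes the expansion 1:1, stratified by site, eye dryness and inferior staining, and leaves Cohorts 1 to 3 unstratified.

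**Analysis.** The sample-size text (Synopsis, Protocol 12.1, SAP 5) states: "In Stage 1 the number of expected enrolled subjects varies between 43 and 53 subjects in the active group", and gives the vehicle range as 37 to 47. The mITT population (SAP 7.1) takes every randomised subject with a baseline and at least one post-baseline efficacy assessment. SAP 13.1.1 introduces its model thus: "The following SAS code will be used to run the ANCOVA analysis for each of Stage 1 and Stage 2". The terms are baseline staining, baseline eye dryness and treatment. The supportive t-tests and Wilcoxon tests have no covariates. The SAP recognises a design phase in one place only: in the CMH analysis of the combined data, "the study Stage will also be included as a stratification factor" (SAP 13.2.1 and parallel sections). The SAP 20 tables are labelled by stage, never by cohort.

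**Use.** The DRC reviews Stage 1 safety and efficacy before recommending Stage 2 (Protocol 6.1). At final analysis the stages are analysed separately and combined, with significance at two-sided p < 0.05 (Protocol 12.4.8).

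**The concern.** The lead-in and the expansion are separate randomisations, run one after the other at different ratios. Within each, treatment is independent of everything else about the patient. Once they are merged without a phase term, treatment is correlated with phase, because a lead-in patient is four times as likely to be on active as on vehicle. Any difference in outcome between the phases that the two baseline covariates do not capture is then partly credited to, or charged against, the drug. Such a difference could come from expectation under 4:1 allocation, from early experience with the procedures, or from who is recruited first. The documents neither report one nor rule one out.

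The Stage 1 estimate is one input to the Stage 2 recommendation and is tested in its own right at the end. A Stage term in the combined analysis would not repair it, because the imbalance lies inside Stage 1.

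**Working it through.** **Inputs.** Target difference and SD: "detecting a 0.35 unit difference between the active and vehicle groups, assuming a standard deviation of 0.75". Dropout 10%. Two-sided alpha 0.05 (Protocol 12.4.1). Cohort sizes from Protocol 6.1.

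**The plan's own figure.** 103 × 0.9 = 92.7 and 67 × 0.9 = 60.3 give the stated 93 and 60. With a difference of 0.35 and SD 0.75, the two-sample t-test then has 80.0% power (80.5% by normal approximation). The stated 80% is reproduced.

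**Are the cohorts pooled?** 8 + 45 = 53 and 2 + 45 = 47; 8 + 35 = 43 and 2 + 35 = 37. These are the ends of the stated ranges. No sentence says the cohorts are pooled, but the arithmetic, the mITT definition and the table list agree.

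**How much leaks.** Let D be the lead-in minus expansion difference in mean change that the covariates do not explain. With phase omitted,

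bias = (lead-in share of active − lead-in share of vehicle) × D.

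| Path | Active/vehicle | Lead-in share, active | Lead-in share, vehicle | Leak |
|---|---|---|---|---|
| Cohort 1 | 53/47 | 8/53 = 15.1% | 2/47 = 4.3% | 10.8% |
| Cohort 2 | 48/42 | 8/48 = 16.7% | 2/42 = 4.8% | 11.9% |
| Cohort 2, with the Cohort 1 TID vehicle patients pooled | 48/44 | 8/48 = 16.7% | 4/44 = 9.1% | 7.6% |
| Cohort 3 | 43/37 | 8/43 = 18.6% | 2/37 = 5.4% | 13.2% |

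The third row arises because mITT takes all randomised subjects and comparisons match on dosing frequency. The SAP does not say whether those two patients join, and 44 lies within the stated vehicle range.

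**What that means for assumed D.** D is not in the documents, so a range is shown. The standard error is 0.75 × √(1/nA + 1/nV) after 10% dropout: 0.158 at 53/47, 0.167 at 48/42 and 0.177 at 43/37. Two-sided error = Φ(−1.96 + bias/SE) + Φ(−1.96 − bias/SE). The table covers leaks of 10.8% to 13.2%.

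| Assumed size of D | Bias (units) | Share of 0.35 | Two-sided type I error |
|---|---|---|---|
| 0.2 SD = 0.15 | 0.016–0.020 | 5–6% | about 5.1% |
| 0.5 SD = 0.375 | 0.041–0.050 | 12–14% | 5.8–5.9% |
| 1 SD = 0.75 | 0.081–0.099 | 23–28% | 8.1–8.6% |

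Simulation (40,000 trials per scenario, no dropout, no covariates) gave lower errors for the unadjusted test: 5.4% and 5.7% at D = 0.35, and 6.9% and 7.6% at D = 0.75, for 53/47 and 43/37. The omitted shift also inflates the residual variance, so the table errs on the high side.

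Power moves as well. At 53/47 with a true effect of 0.35, simulated Stage 1 power goes from 63.7% to 71.6% if lead-in patients improved by 0.35 more, or to 53.0% if they improved by 0.35 less.

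**Combined data.** Simply pooled with Stage 2 at 60 active and 30 matched vehicle, the leak is 8/113 − 2/77 = 4.5% or 8/103 − 2/67 = 4.8%. At 0.5 SD that is 0.017 to 0.018 units and an error of about 5.2%.

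**With a phase factor.** The information n1·n2/(n1 + n2) at 53/47 is 24.91 pooled and 1.6 + 22.5 = 24.10 within phase, so the SE ratio is √(24.91/24.10) = 1.017. At 43/37 it is √(19.89/19.10) = 1.020. Simulated bias falls to about 0.001 and type I error to between 4.9% and 5.2%. Normal-approximation power before dropout goes from 64.4% to 63.0% at 53/47 and from 54.8% to 53.2% at 43/37.

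**The case against.** The strongest reply is that the harm depends on a number nobody has. Both phases share eligibility, vehicle run-in, visit schedule and masking, at no more than two sites, and baseline staining and dryness are already in the ANCOVA. A 1 SD phase effect would be more than twice the effect the drug is hoped to show. All of that stands, and it is why the sizes above are conditional.

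The direction is also open. A 4:1 ratio might raise expectation, although the passages on allocation and masking do not say that patients are told it, and early use at the sites might just as well worsen lead-in results. A reader might infer a bias in favour of the drug; the documents do not support a sign.

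A reader might also quote the one-sided error, which at 0.5 SD goes from 2.5% to 4.4–4.6% and looks like a near doubling. The plan says: "All primary and secondary analyses will be two-sided at a significance level of 0.05". On that basis the figure is 5.8–5.9%.

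Finally, SAP 8.5 calls all efficacy analyses exploratory, no significance is declared at the interim, and the study is powered on the combined data, where the leak is under 5%. This limits the consequence but does not remove it: Protocol 12.4.8 still provides a separate Stage 1 analysis and a significance rule at the end. The DRC analysis plan (Protocol 6.3) is not among the documents and might handle phase at the interim, but it would not change the SAP's final Stage 1 model.

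**Conclusion.** The point holds as a small, avoidable bias. About 11% to 13% of any unexplained lead-in minus expansion difference enters the Stage 1 estimate; on the Cohort 2 path the figure is 11.9%, or 7.6% if the Cohort 1 TID vehicle patients are pooled. For shifts up to 0.5 SD the bias is at most 0.050 units. This rests on pooling inferred from the counts, the mITT definition and the table list, and on an assumed shift.

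Two stronger readings are not supported. One is that the bias could manufacture the target effect: D would have to be 0.35/0.132 = 2.7 to 0.35/0.108 = 3.2 units on a scale from 0 to 4. The other is that the Stage 2 decision rests on this estimate: the DRC also weighs safety and tolerability, and efficacy is one input.

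The case for change is that the analysis should follow the groups in which patients were randomised, and that doing so costs almost nothing.

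**What to change.** 1. In SAP 13.1.1 to 13.1.5, add randomisation phase (lead-in or expansion) as a factor in the Stage 1 ANCOVAs. In the combined ANCOVA, use three levels: lead-in, expansion, Stage 2. Cost: one model term and a Stage 1 standard error 1.7% to 2.0% larger.
2. For the CMH tests, add a single lead-in stratum to the four expansion strata. Crossing phase with all four would spread two vehicle patients over four lead-in cells, so at least two cells would have no vehicle patient and contribute nothing.
3. Show an expansion-only analysis as a sensitivity analysis. It is not equivalent to the adjusted model: it drops ten randomised patients, and its standard error is 5.2% to 6.6% larger than the pooled one (0.1581 against 0.1503 at 45 per arm; 0.1793 against 0.1682 at 35).
4. State whether the Cohort 1 TID vehicle patients join the vehicle group on the Cohort 2 path.
5. As an editorial matter, reconcile the plain 1:1 ratio given for Stage 1 in Protocol 6.1 with the 4:1 lead-in and 1:1 expansion in 10.1.5. The 8:2 cohorts later in 6.1, and SAP 3.1, already follow the latter.
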